III: Tertiary outcomes (already funded in Grant ID 571309: no new funding requested)

Page 60 of 81

Short term outcomes including in-hospital mortality and morbidity at 36 weeks corrected gestation. **Eligibility:**

The sole eligibility criterion is enrolment in the APTS trial, which included parental consent for childhood follow up to 3 years. (Specific eligibility criteria for recruitment to APTS were: mothers imminently delivering babies of 29⁶ weeks gestation or less; informed consent received from a parent; no indication or contraindication to placental transfusion, in view of parent or doctor).

Intervention:

- (a) immediate cord clamping (< 10 seconds after birth)
- (b) deferred cord clamping (≥ 60 seconds after birth)

Sample size and power:

1,320 infants gives 80% power to show a decrease of 8.5% in the primary outcome, from 30% to 21.5%, with two tailed significance of p <0.05, based on a non-adherence rate of 20% (5% in the early clamping group and 15% in the deferred cord clamping group).

Predefined subgroups:

Gender: male or female

Gestational age: infants of 26 6 weeks gestation or less or 27 0 weeks gestation or more

Statistical analysis:

[name], NHMRC Clinical Trials Centre, is statistical lead. Using similar methodology as in our *New England Journal of Medicine* study,¹¹ before unblinding, ASQ scores will be calibrated against Bayley-III cognitive scores obtained concurrently by trained assessors in a random sample (stratified by gestation at birth) of 15% of survivors aged 2 to 3 years (n = ~180). Assuming a 20% event rate and a true area under the ROC curve (AUC) of 0.89 (similar to the result of our previous analysis with the PARCA-R,^{11,45}) a sample of N=180 would yield an estimate of AUC with a 95% confidence interval ranging from 0.83 to 0.93. A cut-off score on ASQ corresponding to 2SD below the Bayley-III norm for the sample (i.e. moderate to severe delay) will be applied to the whole trial.

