2.5.2 Definition of major disability

Follow-up assessments should be performed on all APTS babies eligible for follow-up using the short health status questionnaire (SHSQ) and the Ages and Stages Questionnaire (ASQ-3). Additionally, some sites routinely use the Bayley scales of Infant and Toddler Development – Third edition (Bayley-III) which has been collected where available.

Major disability is defined by one or more of the following:

- Cerebral palsy with an inability to walk unassisted at or after 2 years corrected age,
- Severe visual loss (legally blind i.e. corrected acuity <6/60 in both eyes),
- Deafness, requiring a hearing aid or cochlear implants,
- Major problems with language or speech at or after 2 years corrected for gestation defined by the inability to use more than 10 words (including signed words)
- Cognitive delay as defined below.

A tiered approach (Table 2) will be used in order to obtain a disability status for as many babies as possible. If the data is not available for Tier 1, the disability status will be obtained from Tier 2, otherwise Tier 3. A central review blinded to treatment will be performed as appropriate and all of the information available at any time (i.e. Bayley-III) will be reviewed. If the outcome for an infant is not available from tier 1 or 2 results and can then not be ascertained with a central review, the primary outcome for this infant will be missing.

August 2020

Page 7 of 17

Page 71 of 81

APTS FU Statistical Analysis Plan v2.2

Table 5: Identification of major disability⁺

Disability type	Tiers to move through in order to determine disability status	Definition of Disability present within each tier	Definition of Disability absent within each tier
Cerebral palsy	Tier 1: SHSQ competed after 22 months.	'CP = Yes' and the inability to walk unassisted	'CP = No' or 'CP=Yes' but only an unsteady walk
	Tier 2: ASQ-3 completed after 18 months	Score of 0 for Gross Motor domain	Score >0 for gross motor domain
	Tier 3: Central review required		
Severe visual loss	Tier 1: SHSQ completed at any age	Legally blind = Yes	Legally blind = No
	Tier 2: Central review required		
Deafness	Tier 1: SHSQ completed at any age	Hearing loss = Yes with requirement for hearing aids	Hearing loss = No or Hearing loss = Yes with no requirement for hearing aids
	Tier 2: Central review required		

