Major problems with language or speech	Tier 1: SHSQ completed between 22-27 months (inclusive)	Unable to speak 10 words	Able to speak >10 words
	Tier 2: ASQ-3 completed after 18 months	Communication score indicative of delay (based on published ASQ cut-off)	Communication score not indicative of delay (based on published ASQ cut-off)
	Tier 3: Central review		
Cognitive delay	Tier 1: ASQ-3 completed after 18 months	Problem solving score indicative of delay (based on published ASQ cut-off)	Problem solving score not indicative of delay (based on published ASQ cut-off)
	Tier 2: Central review		

⁺ the windows given above for the determination of disability using the various sources were determined by clinicians involved in the APTS Follow-up study. All ages are corrected ages.

If the baby is alive and does not have one of the above major disabilities, and has been assessed for all of the above components, then they will be classified as alive and disability free. If the infant was alive and has no disability for CP, severe visual loss, deafness and major problems with language or speech, but missing information for cognitive delay, then the infant will be assumed to be alive and disability free at 2 years. Otherwise the infant will be considered as missing for the primary analysis.

Page 8 of 17

Page 72 of 81

APTS FU Statistical Analysis Plan v2.2

Table 6: Summary of completeness of the primary outcome and its components

Endpoint	Complete data	Missing data
Death or disability at 24 months		
Death status		
Cerebral palsy ⁺		
Severe visual loss+		
Deafness [†]		
Major problems with language or speech ⁺		
Cognitive delay ⁺		
hese analyses are restricted to those that were as	ssessed for these outcon	nes

Additionally, the baseline characteristics will be compared between those that have outcome data at 24 months versus those that have missing data at 24 months.

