2.6.4 Multiple imputation analysis

A multiple imputation analysis^{1,2,3} using chained equations⁴ will be conducted for the primary outcome as a sensitivity analysis. Covariates to be included in both the imputation stage and the modelling stage include: treatment, gestational age (<27 weeks vs \geq 27 weeks), gender, birthweight (into quartiles), multiple birth (singleton vs multiple birth) and mode of delivery (vaginal versus caesarean).

August 2020

Page 12 of 17

Page 76 of 81

APTS FU Statistical Analysis Plan v2.2

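### A survivor negative on four disability components but with no cognitive result is counted as disability free, and the planned multiple imputation does not test that assumption

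*Supplement*

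**What the plan says.** All references are to SAP v2.2 unless stated.

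- **Components.** Section 2.5.2 defines major disability as any one of cerebral palsy without independent walking, severe visual loss, deafness, major language or speech problems, or cognitive delay.
- **Sources (Table 5).** The short health status questionnaire (SHSQ) is the first source for the first four components. Cognitive delay has only the ASQ-3 problem-solving score and then central review.
- **General rule (before Table 5).** When tiers 1 and 2 do not supply the outcome and it "can then not be ascertained with a central review, the primary outcome for this infant will be missing".
- **Specific rule (below Table 5).** A living child with no disability on the first four components "but missing information for cognitive delay, then the infant will be assumed to be alive and disability free at 2 years". The next sentence is "Otherwise the infant will be considered as missing for the primary analysis".
- **Imputation (2.6.4).** Multiple imputation by chained equations "will be conducted for the primary outcome as a sensitivity analysis". The listed covariates are treatment, gestational age, gender, birthweight, multiple birth and mode of delivery. No disability component, SHSQ item or ASQ score is listed.

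**The concern.** The specific rule fills in a missing component with its most favourable value and then treats that value as observed. A child with an SHSQ in the required window but no usable ASQ-3 can reach it whenever central review is inconclusive. The reverse case is handled differently: a child with an ASQ-3 but no vision or hearing result, and nothing positive elsewhere, is missing.

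The two statements in 2.5.2 also point different ways for the same child. Central review is the last step for cognition. After it fails, the general rule, read alone, makes the outcome missing, while the specific rule makes it a non-event.

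The planned imputation would not expose the consequence. A child already coded as a non-event has nothing to impute. Section 2.6.4 does not say whether it imputes the composite or its components, so this is an inference, but it names only the primary outcome and lists no component. The adjusted and adherence-weighted analyses use the same outcome variable, and the secondary outcome major disability appears to carry the same coding.

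What is at stake is mainly the comparison between arms. The trial is open label and the first source for cognition is a parent-completed form. If missing cognitive results differ between arms, the rule turns that difference into an apparent treatment effect favouring the arm with more of them.

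**Working it through.** **The plan's own figure.** SAP Table 1 claims 80% power with 1,350 infants for 35% against 25%, allowing for 30% non-compliance. I used a two-sided 0.05 test with 675 per arm, pooled variance under the null and independent infants.

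- All dilution in the delayed-clamping (DCC) arm: the difference is 0.7 × 10 = 7 points, so 35% against 28%. Then z = (0.07 × √675 − 1.96 × √(2 × 0.315 × 0.685)) / √(0.35 × 0.65 + 0.28 × 0.72) = 0.81, and power is 79.1%.
- A 15% crossover in each arm: 33.5% against 26.5%, and power is 80.2%.

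All six rows fall between 78.6% and 80.2%. The table reproduces and is not in question. It supplies the base risks used below.

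**Inputs for the rule.** Let m be the share of infants who are negative on four components with no cognitive result, and q their true risk of cognitive delay. Neither is in the documents. I assume m = 2–15% and q = 5–20%. The recorded risk is then the true risk minus m × q.

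**Equal m in both arms, true risks 35% and 28% (RR 0.800), N = 1,350**

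| m | q | events hidden (1,350 × m × q) | recorded RR | nominal power |
|---|---|---|---|---|
| 2% | 5% | 1.4 | 0.799 | 79.2% |
| 5% | 10% | 6.8 | 0.797 | 79.5% |
| 10% | 20% | 27.0 | 0.788 | 80.6% |
| 15% | 20% | 40.5 | 0.781 | 81.4% |

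For the last row, (0.28 − 0.03)/(0.35 − 0.03) = 0.25/0.32 = 0.781.

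**Unequal m, no true effect, 35% in both arms, 675 per arm.** With s = recorded difference / √(2p̄(1 − p̄)/675), where p̄ is the mean recorded risk, type I error = 1 − Φ(1.96 − s) + Φ(−1.96 − s).

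| m, immediate clamping (ICC) | m, DCC | q | spurious RR | type I error |
|---|---|---|---|---|
| 5% | 10% | 5% | 0.993 | 0.051 |
| 5% | 10% | 10% | 0.986 | 0.054 |
| 5% | 10% | 20% | 0.971 | 0.068 |
| 5% | 15% | 5% | 0.986 | 0.054 |
| 5% | 15% | 10% | 0.971 | 0.067 |
| 5% | 15% | 20% | 0.941 | 0.122 |

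For the last row, the recorded risks are 0.34 and 0.32, the standard error is √(2 × 0.33 × 0.67/675) = 0.0256, and s = 0.78. With 10% missing under ICC and 5% under DCC, the RR is 1.007 to 1.030.

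**What dropping these children would do.** Deaths, and children positive on any component, stay in whatever their cognitive status. Removing only survivors negative on four components therefore raises the composite by m × (0.35 − q)/(1 − m). Take 10% of survivors with 10% mortality assumed, so m = 0.10 × 0.90 = 9% of infants.

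| q | shift under the rule (−m × q) | shift if dropped |
|---|---|---|
| 10% | −0.9 points | 0.09 × 0.25/0.91 = +2.5 points |
| 20% | −1.8 points | 0.09 × 0.15/0.91 = +1.5 points |

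With no true effect and 5% against 10% of survivors affected (4.5% against 9% of infants), the false difference between arms is:

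- q = 10%: 0.045 × 0.10 = 0.45 points under the rule; 2.47 − 1.18 = 1.3 points if dropped.
- q = 20%: 0.9 points under the rule; 1.48 − 0.71 = 0.8 points if dropped.

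**The case against.** The strongest reply is that the rule is narrow, deliberate and close to harmless. These children have four of five components settled, and a treatment-blinded central review of everything available, including any Bayley-III, comes first. A negative language result probably lowers their risk of isolated cognitive delay. The summary of changes says the SAP was finalised before unblinding and before any analysis. No document suggests that ASQ-3 return differs by arm. All of this stands, and it limits the size of the problem. It does not bring the risk of delay to zero or supply an analysis that varies the assumption.

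Four stronger readings are tempting, and the documents do not support them:

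- **That 2.5.2 flatly contradicts itself.** The general rule speaks of the infant's outcome, not of each component. The later text can be read as a specific exception followed by the residual category. A clarifying sentence is needed.
- **That about 20% of these children have cognitive delay.** The phrase "Assuming a 20% event rate", in the statistical analysis section of the follow-up funding application, is an input to the precision of a ROC area. It concerns a calibration sample stratified by gestation, and SAP 2.8 says sampling aimed for high risk. It is not the risk in children negative on the other four components.
- **That no planned table would show the problem.** Table 6 counts missing cognitive results overall. Table 7 gives cognitive delay by arm among those assessed, so an imbalance would show in its denominators. Neither isolates the affected children or corrects the primary estimate.
- **That the exception should be deleted.** In a complete-case analysis this discards likely non-events. It does more harm than the rule at a 10% delay rate and is roughly equal at 20%.

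**Conclusion.** The point holds as a gap in the sensitivity analysis and an unclear definition. It does not show that the primary analysis is invalid. Best-case imputation of one component enters the primary outcome as observed data, and the imputation in 2.6.4, as written, leaves it untouched.

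Its size cannot be fixed from the documents. Over the assumed ranges, balanced missingness hides roughly 1 to 41 events among 1,350 infants and shifts the relative risk by at most about 0.02, slightly away from 1. An imbalance of 5–10 points matters more: when DCC has more missing results and there is no true effect, the relative risk runs from 0.993 to 0.941 and type I error from 0.051 to 0.122. The last figure needs both 5% against 15% missing and a 20% delay rate. The calculations ignore clustering within multiple births.

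**What to change.** 1. In 2.5.2, state that the rule below Table 5 is a specific exception to the general rule above it, applying only after central review has failed to settle cognition.
2. In 2.6.4, set the cognitive component of these children to missing. Impute it from their known components, treatment and the listed baseline covariates. Then rebuild both the composite and major disability from the imputed component.
3. Report the number of such children by arm, for example as an added row in Table 6 split by arm.
4. Keep these children in the primary analysis as now defined; do not drop them from the complete-case set.

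The cost is SAP wording and a modest amount of extra analysis. No new data are needed. The imputed result still assumes that, given the other components and covariates, children without a cognitive result resemble those with one, and the report should say so.

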2.2 Follow-up cohort

Table 2: Children with follow-up data available

	Immediate cord clamping	Delayed cord clamping					
Total babies randomised	816	818					
Babies not included in ITT							
 Ineligible babies (born >30 weeks) 	27	27					
• Withdrawn consent (prior to delivery)	2	2					
Stillborn babies	5	5					
Babies included in main study ITT	782	784					
Babies removed because included in the pilot study							
Babies available for the APTS Followup study							
No follow-up obtained	No follow-up obtained						
Partial follow-up obtained, but incomplete							
Data available for primary outcome at 24 months							

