2.5 Outcome definitions

The primary outcome is death and/or major disability at 24 months corrected age. Assessments of major disability must be performed between 18 months to 27 months. Any data outside of this window will require a central review.

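### A survivor still lacking a non-cognitive component counts as an event if anything assessed is positive but goes missing if all is negative, while one lacking only cognition is assumed disability free

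*Supplement*

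**What the plan says.** All references are to SAP v2.2. Section 2.5 sets the endpoint: "The primary outcome is death and/or major disability at 24 months corrected age". Section 2.5.2 then applies these rules to living children.

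- **Event.** "Major disability is defined by one or more of the following": cerebral palsy, severe visual loss, deafness, language or speech problems, cognitive delay. Complete assessment is not required.
- **Non-event, general rule.** The child has no disability "and has been assessed for all of the above components, then they will be classified as alive and disability free".
- **Non-event, exception.** This applies when the four non-cognitive components are all known and negative and only cognition is unknown. The text reads: "but missing information for cognitive delay, then the infant will be assumed to be alive and disability free at 2 years".
- **Remainder.** "Otherwise the infant will be considered as missing for the primary analysis".

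Table 5 gives the sources. For both vision and deafness the entry is "Tier 1: SHSQ completed at any age", and the next tier is central review. Cerebral palsy and language can come from the SHSQ within an age limit or, failing that, from the ASQ-3. Cognition comes from the ASQ-3 and then central review. The review is blinded to treatment and may use information from any time.

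Table 2 (section 2.2) has a row, by arm, for "Partial follow-up obtained, but incomplete". Section 2.6.4 plans multiple imputation of the primary outcome as a sensitivity analysis, with treatment and baseline covariates listed.

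**The concern.** For a child lacking a non-cognitive component, entry to the primary analysis depends on the result. Take a family that returned the ASQ-3 but has no SHSQ. If the ASQ-3 shows delay, the child is an event. If it is normal, the child needs central review to supply vision and hearing, and is missing if it cannot. Yet that second child is nearly a known non-event, since only two components are open.

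The exception for cognition works the other way. A child with an SHSQ at 22 to 27 months and no ASQ-3 is counted as disability free, although cognitive delay was never looked for.

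At stake are the level of the composite in each arm and, if partial follow-up differs between arms, the relative risk. The trial is open label (section 1.2), so equal partial return is likely but not guaranteed. The planned imputation lists no component results, so it would not use what is already known about these children.

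**Working it through.** **1. Plan figure.** The point disputes no number in the SAP. The planning rates do reproduce: Table 1, first row (35% to 25%, N = 1350, 30% non-compliance). The diluted difference is 0.70 × 10 = 7 points, so 35% against 28% with 675 per arm. Two-sided 0.05 gives z = (0.07√675 − 1.96√(2 × 0.315 × 0.685)) / √(0.35 × 0.65 + 0.28 × 0.72) = 0.81, a power of 79% against 80% stated.

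**2. Patterns.** Five components give 2⁵ − 2 = 30 partly assessed patterns. In 29, any positive is an event and all negative is missing. In one (only cognition missing), all negative is a non-event. That one is a natural pattern, so the count says nothing about frequency.

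**3. ASQ-only children.** No rates are given in the documents, so these are assumptions: mortality 10%; disability 25% in fully assessed survivors; in ASQ-only survivors, 20% with ASQ delay and a further 1% with vision or hearing loss. Let *a* be the share of survivors who are ASQ-only and *r* the share of ASQ-normal ones resolved by central review.

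- True = 0.1 + 0.9[(1−a)0.25 + a·0.21]
- Observed = {0.1 + 0.9[(1−a)0.25 + a(0.20 + 0.01r)]} / {0.1 + 0.9[(1−a) + a(0.20 + 0.80r)]}

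For a = 10%, r = 0: 0.3205/0.928 = 34.5%, against 32.1% true.

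| a | True | r = 0 | r = 50% | r = 80% |
|---|---|---|---|---|
| 5% | 32.3% | 33.5% (+1.2) | 32.9% (+0.6) | 32.5% (+0.2) |
| 10% | 32.1% | 34.5% (+2.4) | 33.3% (+1.2) | 32.6% (+0.5) |
| 15% | 32.0% | 35.7% (+3.7) | 33.7% (+1.8) | 32.6% (+0.7) |

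**4. Relative risk with unequal shares** (arm with 5% over the other arm):

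| Shares | r = 0 | r = 50% | r = 80% |
|---|---|---|---|
| 5% v 10% | 0.97 | 0.99 | 1.00 |
| 5% v 15% | 0.94 | 0.98 | 1.00 |

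The true ratios here are 1.01 rather than exactly 1, because ASQ-only children were given 21% disability and the others 25%.

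**5. Equal shares, and the cognition rule.** Take true risks of 35% and 25% (true RR 0.714), of which deaths are 10% and 7%. Let 2% to 15% of survivors be partly assessed, and let a truly disabled one show a positive among the assessed components with probability *s* from 0.3 to 0.8. These too are assumptions.

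- *Non-cognitive component missing* (share m): events = deaths + disabled × [(1−m) + m·s]; non-events = free × (1−m). At m = 15%, s = 0.8: 0.3425/(0.3425 + 0.5525) = 38.3%. Over the range, the risks read 35.2% to 38.3% and 25.2% to 27.7%, and the RR is 0.715 to 0.725.
- *Only cognition missing*: events as above, and every other survivor is a non-event. At 15%, s = 0.3: 0.10 + 0.25(0.85 + 0.045) = 32.4%. Over the range, the risks read 32.4% to 34.9% and 23.1% to 24.9%, and the RR is about 0.714.
- *Both at 5%, s = 0.5*: 35.1% and 25.2%. The two errors nearly cancel.

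**The case against.** The strongest reply is that the ASQ-only child is sent to central review by design. That review is blinded and unrestricted in its sources, and only children it cannot resolve are missing. The zero-recovery column is therefore an extreme. This stands, and is why a range is shown. It does not remove the problem, because section 2.5.2 itself foresees outcomes that review cannot settle.

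A second reply is that the trial estimates a relative risk, and with equal missingness the relative risk is almost right. This also stands. Nothing in the documents shows a difference between arms. The follow-up grant application (section 5.2) notes that parents know the allocation and argues that reporting bias is unlikely.

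Several stronger readings are tempting but not supported:

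- *Partly followed children never add non-events, so the event rate is overstated.* The cognition exception contradicts the first half, and its bias runs the other way. The net direction is unknown.
- *Any partly assessed, all-negative child is close to a known non-event.* This fits the ASQ-only child. It does not fit a child with only an early SHSQ, for whom cerebral palsy, language and cognition are all unknown. Setting that child to missing is defensible.
- *Section 2.6.4 will impute such children at the average risk.* The section does not say whether the composite or its components are imputed, and it conditions on gestation, birthweight and other covariates. What can be said is that it lists no component results.

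Part of the reporting remedy already exists. Table 2 shows partial follow-up by arm, Table 6 shows missingness by component, and baseline characteristics are compared by outcome availability. None of these separates any-positive from all-negative children.

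**Conclusion.** The asymmetry is real but limited. It concerns survivors still lacking cerebral palsy, vision, deafness or language after central review. That a positive one counts as an event is implied by the definition rather than stated beneath Table 5. Read literally, the closing sentence there could make such a child missing. The opposite treatment of missing cognition means that no net direction can be claimed.

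The ASQ-only effect taken alone is 0.2 to 3.7 points on the composite, depending on the assumed share (5% to 15%) and central-review recovery (80% to none). The relative risk is nearly unaffected when shares are equal. It reaches about 0.94 only with 5% against 15% and no recovery, and about 0.98 with half recovered. The follow-up tables are blank templates, so none of these shares can be checked. This is a worthwhile, inexpensive improvement to the plan and not evidence that the primary result is wrong.

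**What to change.** 1. In 2.5.2, state explicitly how a partly assessed child with a positive component is classified.
2. In 2.6.4, impute the missing components, cognition included, among known survivors. Condition on the components already observed and on the listed covariates, and then derive the composite. An ASQ-normal child is then imputed only for vision and hearing, and an SHSQ-only child is no longer assumed free of cognitive delay.
3. Report partly assessed children by arm, split into any positive and all negative, with the number resolved by central review.
4. Optionally, add a sensitivity analysis limited to deaths plus survivors assessed on all components. Say that it drops children whose disability is already known, so it has a selection problem of its own.

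The cost is SAP wording, a little more programming and a more complex imputation model. No new data are needed.
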